D6.3. Covariate, Predictor, and Determinant Measures. Participant self regulation will be reported by the classroom teacher and parent/guardian of each child prior to and following each summer.[91] Children will also complete a similar COMPSCALE – Short Form, an 18-item survey that rates their ability to self-regulate.[92] The parent/guardian of each child will also complete a survey that covers rules for bedtime, the home food environment, social support for physical activity, and child dietary intake. Survey questions are from established surveys used to investigate the influence of parents on the health behaviors of their children. To account for environmental factors associated with accelerated weight gain or fitness loss, the obesogenic nature of participating children's/families' neighborhood environments will be assessed using measures that are consistent with other recent, large-scale studies of environmental influences on physical activity and nutrition.[93-96] These measures include walkability (e.g., net residential density, intersection density, land use mix, and retail floor area ratio),[97] the number of parks (and total park acreage) and the number of public (e.g., municipal community center), non-profit (e.g., YMCA), and private (e.g., indoor soccer complex) recreation facilities using publicly-available sources,[93, 94] crime data,[98, 99] neighborhood food,[93, 94, 96] and neighborhood-level disadvantage.[100]

D6.4. Process Implementation Outcomes. Detailed process/implementation data will be captured. Specifically, for each child randomized to the Voucher Program or the comparison/control group, information regarding their attendance at a summer day camp will be collected. For the Voucher Program group in the summer of Y01 and Y02, detailed information will be collected regarding the programmatic offerings occurring at the camps, [101-108] and types of foods and beverages served.[109-112]

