D8.2. Statistical Models. To test the hypothesis in **Aim 1** and **Aim 2**, repeated measures linear and non-linear mixed models accounting for repeated measures within children and children within schools will be estimated. Group, time, setting (i.e., school vs. summer) and all 2-way and 3-way interactions will be included, with the group-x-time-x-setting interaction as the primary contrast of interest. Structural equation models will also estimate the mediating pathways of the obesogenic behaviors on zBMI change.

D8.3. Sex as a Biological Variable. Because girls and boys have been shown to engage in differing levels of obesogenic behaviors and to have differing levels of fitness and prevalence of overweight and obesity, all models will include sex (i.e., boys vs. girls) and age as covariates. Including sex as a covariate in models will preserve the statistical power of the study while allowing for the examination of sex as a biological variable.

D9. Group Assignment. The unit of randomization will be at the child level. The two conditions will be: 1) Intervention - children receiving a voucher for a summer day camp and 2) Control - no summer day camp voucher. Children will be randomized (using a random number generator) by stratifying them based on grade and gender to ensure equal numbers across the age range and boys and girls in each of the two conditions.

D10. Timeline. A project timeline is provided in Clin-Trls Section 2, Extended Study Timeline.

D11. Limitations and Benchmarks of Success. One key to success will be the study retention of children/families over time. To address this, the measures have been modified based on piloting with comparable individuals and incentives are planned for participation. Another key issue is whether children receiving vouchers attend the day camp during the designated summer. Children in the intervention condition who fail to attend the camp would obviously not be exposed to the independent variable. However, the Recreation Commission has observed that high community demand for summer programming, coupled with ease of access because the camp is centrally located, makes attendance likely. Further, camp attendance (and lack thereof) will be tracked to explore possible barriers to attendance.

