D8.2. Statistical Models. To test the Aims, analytical modeling that capitalizes on the richness of the data set will be utilized. To test the hypothesis in Aim 1, repeated measures linear and non-linear mixed models accounting for repeated measures within children and children within schools will be estimated. Group, time, setting (i.e., school vs. summer) and all 2-way and 3-way interactions will be included, with the group-x-time-x-setting interaction as the primary contrast of interest. For Aim 2, the differences in obesogenic behaviors over time will be evaluated using the same repeated measures linear and non-linear mixed models. Structural equation models will be estimated to evaluate the mediating pathways of the obesogenic behaviors on the amount of change occurring in zBMI over time between the two groups.

D8.3. Sex as a Biological Variable. Because girls and boys have been shown to engage in differing levels of obesogenic behaviors and to have differing levels of fitness and prevalence of overweight and obesity, all models will include sex (i.e., boys vs. girls) and age as covariates. Including sex as a covariate in models will preserve the statistical power of the study while allowing for the examination of sex as a biological variable.

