D8.4. Missing Data. Across this study, four scenarios with missing data are possible: 1) missing items within children; 2) missing cases (i.e., children not present to complete assessments); and whether the missingness is for 3) missing determinants/covariates or 4) missing outcomes (e.g., zBMI, physical activity). For missing assessments, such as incomplete diaries, parent surveys, accelerometer data, or BMI, the parents will be contacted and, where willing, they will be invited to re-complete the missing assessments. Where children are not present at the school on days of BMI assessments or to pick-up their monitor and surveys, data collectors will return to the camp on another day to complete the assessments. For any assessments not obtained, models will be estimated using full information maximum likelihood estimators, as well as employ multiple imputation techniques. These two strategies for handling missing outcome data will be compared (analogous to a sensitivity analysis) to determine the most appropriate way to handle the missingness. Based on previous large-scale group randomized trials,[102, 131] full information maximum likelihood estimators provide a robust and unbiased estimate. This is consistent with literature comparing this estimator to models using multiple imputation.[132] For missing determinant/covariates that are continuous, multiple imputations will be employed. For missing determinant/covariates that are categorical, a missing dummy variable technique will be used rather than imputing categorical data.[133, 134]

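### The missing-dummy rule for categorical covariates can leave residual confounding in the mediation model if an incomplete categorical confounder enters it; the randomised contrasts are not affected

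*SAP*

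**What the plan says.** SAP D8.4 treats incomplete determinants and covariates by type. For continuous ones: "For missing determinant/covariates that are continuous, multiple imputations will be employed". For categorical ones: "a missing dummy variable technique will be used rather than imputing categorical data". The rule is general and no model is excepted. The only comparison of missing-data methods in D8.4 concerns outcomes: "These two strategies for handling missing outcome data will be compared (analogous to a sensitivity analysis". Nothing in the plan therefore tests the dummy rule.

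SAP D8.2 plans more than the arm comparison: "Structural equation models will be estimated to evaluate the mediating pathways of the obesogenic behaviors" on zBMI change. On covariates, SAP D8.3 says that "all models will include sex (i.e., boys vs. girls) and age as covariates". It names no other covariate for the mediation model. Protocol D6.3 lists candidates, among them a survey in which the parent "will also complete a survey that covers rules for bedtime, the home food environment, social support for physical activity, and child dietary intake". How those items are coded, and whether they enter the mediation model, is not stated.

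Protocol D9 sets the design: "The unit of randomization will be at the child level", with children randomised "by stratifying them based on grade and gender to ensure equal numbers across the age range".

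**The concern.** A missing dummy gives all children with an unknown value one common intercept. Among those children the covariate is not adjusted for at all. Where arms are randomised and the covariate is a baseline one, this costs a little precision and no validity, because the covariate is unrelated to arm.

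The step from behaviour to zBMI has no such protection. Activity, sleep, screen time and diet are measured after randomisation and are not assigned, so that path is only as good as the covariate adjustment behind it. The same holds for any analysis under exploratory Aim 3B (baseline self-regulation as moderator) that adjusts for categorical covariates.

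At stake is the use of the mediation results. Protocol D12 intends the study to inform which behaviours a follow-on trial should target. Residual confounding would tilt that choice, and a larger sample would not remove it.

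**Working it through.** The documents give no figure on this point, so there is none to reproduce.

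**Inputs from the documents.** 80 children (SAP D8.1); two arms randomised by child (Protocol D9); behaviours as mediators of zBMI change (SAP D8.2); dummy coding for missing categorical covariates (SAP D8.4).

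**Assumptions, not in the documents.** One binary confounder C with prevalence 0.5 shifts both the behaviour M and the outcome Y by g residual SDs. C is missing completely at random with share p. The model is linear and the true M-to-Y path is 0.

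**Step 1: bias with no adjustment.** Since Var(C) = 0.25,

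B = (g²/4) / (1 + g²/4).

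- g = 0.5: 0.0625/1.0625 = 0.059
- g = 0.8: 0.16/1.16 = 0.138
- g = 1.0: 0.25/1.25 = 0.200

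**Step 2: share of B that the dummy leaves.** The fitted slope is a weighted mean of the slope among children with C known (unbiased) and among those with C missing (bias B). The weights follow the residual variance of M in each set, 1 and 1 + g²/4:

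w = p(1 + g²/4) / [p(1 + g²/4) + (1 − p)].

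For g = 1 and p = 0.20: 0.25/(0.25 + 0.80) = 0.238, so the bias is 0.238 × 0.200 = 0.048.

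**Step 3: range.** Bias = w × B. The false-positive rate is from simulation at n = 80, 20,000 replicates per setting, nominal 5%.

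| Shift in M and Y | Bias at 10 / 20 / 30% missing | False-positive rate at 10 / 20 / 30% missing |
|---|---|---|
| 0.5 SD | 0.006 / 0.012 / 0.018 | 4.9 / 5.1 / 5.4% |
| 0.8 SD | 0.016 / 0.031 / 0.046 | 5.3 / 5.9 / 6.8% |
| 1.0 SD | 0.024 / 0.048 / 0.070 | 5.6 / 7.0 / 9.3% |

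At n = 80 the standard error of the path is about 0.116. The bias at 20% missing is thus 0.012/0.116 = 0.10 standard errors for 0.5 SD shifts. At 30% missing and 1 SD shifts it is 0.070/0.116 = 0.60.

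**Step 4: does imputation remove it?** A second simulation set the true path at 0.30, the arm effect on M at −0.40 and the direct arm effect at −0.30, with 10 to 40% missing and n = 80. The mean path was:

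- dummy method: 0.301 to 0.326 (0.5 SD shifts) and 0.314 to 0.364 (0.8 SD shifts)
- multiple imputation of C by logistic regression on arm, M and Y: 0.296 to 0.305

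**Step 5: the randomised contrast.** In that model the true total arm effect is −0.30 + (−0.40 × 0.30) = −0.42. With the dummy, runs at n = 400,000 gave −0.416 to −0.425, within 0.001 of the estimate from complete data in the same runs.

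**The case against.** The strongest reply is that the documents identify no covariate on which the rule would do harm. Harm needs a categorical covariate that is in the mediation model, confounds behaviour and zBMI, and has missing values. Sex, the only categorical covariate named for the models, is a stratification factor and should be complete, as should grade. Age is continuous. The self-regulation scales, if scored in the usual way, are continuous and fall under the imputation rule. The neighbourhood measures are largely densities, counts and acreage and do not depend on survey response. That leaves the parent survey. D8.4 plans to re-contact parents about incomplete surveys, and Protocol D7 pays families $50 for returning devices and the completed summer packet. The 1 SD setting is also extreme: it is more than twice the d of 0.46 that SAP D8.1 derives for the voucher, and it acts on behaviour and outcome together.

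All of this stands, and it makes the point conditional and probably small. It does not remove the point. D8.4 provides for missing categorical covariates, so the plan allows that they will occur, and the chosen method is the weaker one for a non-randomised path.

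Three stronger readings are tempting, and the documents do not support them:

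- **That the primary analysis is biased.** The Aim 1 and Aim 2 contrasts compare randomised arms, and Step 5 shows no bias from the dummy. Within the mediation model, the arm-to-behaviour path is protected in the same way.
- **That a planned set of determinant models is affected.** D8.2 specifies none. Determinants appear as measures in Protocol D6.3 and in the missing-data rule only, and Aim 3B has no stated model.
- **That an inert behaviour is likely to pass as a mediator.** At 0.5 SD the false-positive rate barely moves.

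**Conclusion.** The concern holds in conditional form, as a minor improvement. If an incomplete categorical confounder, for example a categorical parent-survey item, enters the mediation model, the dummy rule leaves about the missing share of its confounding in the behaviour-to-zBMI path: 10 to 12% of it at 10% missing and 31 to 35% at 30%, for shifts of 0.5 to 1 SD. In absolute terms the bias runs from 0.006 to 0.070 over the range shown. It is negligible beside sampling error for a moderate confounder and visible only for a strong one with substantial missingness. The same reasoning carries to an Aim 3B analysis that adjusts for such covariates.

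The direction of the argument does not depend on the assumed figures, but the size does: one binary confounder, prevalence 0.5, equal shifts in behaviour and outcome, values missing completely at random. The plan gives nothing to narrow that range, because neither the mediation model's covariates beyond sex and age nor an expected missing rate is stated.

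**What to change.** In SAP D8.4, limit the dummy rule to baseline covariates in the randomised arm comparison. For the mediation model and any other non-randomised analysis, include categorical covariates in the multiple imputation already planned for continuous ones, using logistic or multinomial models with the mediator and outcome in the imputation model. Alternatively, bring them into the full information maximum likelihood model. It would help to list the mediation model's covariates in D8.2 at the same time, since that shows whether the rule will matter.

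The cost is one sentence, a few more variables in an imputation already planned, and slightly more analysis work. With 80 children, sparse categories may have to be collapsed before imputation.
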